10.3.2.2. Patient Characteristics

Patient's baseline age, sex, race, height, body weight, body mass index, MMSE score, other baseline efficacy measures, previous exposure to antipsychotic treatment, and eGFR value will be recorded. Baseline and demographic characteristics will be summarized using descriptive statistics by treatment arm and overall.

10.3.2.3. Concomitant Therapy

Approved medications will be permitted in this study as described in Section 7.7. Patients who begin such treatments during the study will be summarized.

10.3.2.4. Treatment Compliance

The proportion of patients who are significantly noncompliant, as noted in Section 7.6, may be summarized.

10.3.3. Efficacy Analyses

10.3.3.1. Primary Analyses

The primary objective of this study will be assessed in the Evaluable population by analyzing NPI response rates. Response will be defined using two NPI endpoints: 1) the psychosis domain score, calculated as the sum of the delusions and hallucinations domain scores, and 2) the aggression/agitation domain score. Each domain score is the product of the severity and frequency ratings.

A patient with a 30% improvement from baseline on a subscale will be considered a responder for that subscale. At baseline, patients will be given a diagnosis of psychosis and/or agitation/aggression. A patient with a psychosis diagnosis will be considered an overall responder with a response on the psychosis subscale, a patient with a diagnosis of aggression/agitation will be considered an overall responder with a response on the aggression/agitation subscale, and a patient with both diagnoses will be considered an overall responder with a response on either subscale.

The primary analysis will use a one-sided Fisher's exact test with a 5% type 1 error rate.

10.3.3.2. Secondary Analyses

Secondary efficacy outcomes include CGI-I; NPI Total Score; NPI-Core Total (combination of 3 items: hallucinations, delusions, and agitation/aggression); NPI Caregiver Distress; NPI domain of anxiety.

The delusions, hallucinations, and aggression/agitation domain scores will be added together to form a Core Total score. A patient with a 30% improvement from baseline will be considered a responder on the Core Total score. The treatment groups will be compared using a one-sided Fisher's exact test.

The psychosis and aggression/agitation domain scores, and the Core Total score, will be analyzed as continuous measures.

The change from baseline for quantitative endpoints will be analyzed using repeated measures mixed models assuming data are missing at random, with covariates for baseline and the stratification factors

The CGI-I scores will be analyzed using Cochran-Mantel-Haenszel tests, stratifying by the randomization strata, and using modified Ridit scores (i.e. van Elteren tests).

Details of the analyses of secondary efficacy outcomes will be specified in the SAP.

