Efficacy and Outcome Measures	1 1		I		I	T	ı		1 1	
NPI	xb	xb		X	X	X		X	X	X
CGI-S		X								
CGI-I					X			X	X	X
ZBI-22		X			X			X		
MMSE	X	X			X			X		X
UPDRS Part III		X			X			X	X	X
Laboratory Samples	T T		ı		ı	ı			 	
Clinical chemistry and hematology	X	X		X		X		X		X
Urinalysis	X	X						X		X
Plasma sample collection for PK analysis (see Table 9.1)				x	x	X		X		X
Plasma and serum collection for biomarker research		X				X		X		Х
Blood for epigenetic research		X				X	1	Х		х
Blood for assessment of APOE and		Λ					 	Λ		Λ
HTR2A SNPs ^d		X								
Blood for pharmacogenetic researchd		X								

Study Schedule Protocol MP-101-01 (continued)

Abbreviations: APOE = apolipoprotein E; BP = blood pressure; CGI-I=Clinical Global Impressions of Improvement; CGI-S=Clinical Global Impressions of Severity; C-SSRS= Columbia Suicide Severity Rating Scale; ECG = electrocardiogram; ET = early termination; HIV = human immunodeficiency virus; HTR2A = 5-hydroxytryptamine serotonin 2A receptor; MMSE = Mini-Mental State Examination; NPI = Neuropsychiatric Inventory; PK = pharmacokinetic, SNP = single nucleotide polymorphism; TUG = Timed Up and Go test; UPDRS = Unified Parkinson's Disease Rating Scale; V = visit; Zarit Burden Interview-22= ZBI-22.

- a Phone call.
- b Patients must have at least one of the following at Visit 1 (screening) and Visit 2 (Week 0):
 - o an NPI score of \geq 4 on either delusions or hallucinations individual items
 - o an NPI score of ≥6 on the Psychosis Subscale (combined delusions and hallucinations)
 - o an NPI score of ≥4 on agitation/aggression domain
- c During screening, the "Lifetime/Recent-Clinical" version of the C-SSRS will be used. The "Since Last Visit-Clinical" version will be used for all subsequent assessments.
- d Samples should be collected at V2, if possible, but may be collected at an alternate visit if they cannot be collected at V2.

3. Introduction

MP-101 (formerly known as LY2979165 ammonium monohydrate) is the alanine prodrug of LY2812223, a selective orthosteric metabotropic glutamate (mGlu) 2 receptor agonist. The objectives of Study MP-101-01 are to assess the tolerability, pharmacokinetics (PK), and efficacy of MP-101 in the treatment of patients with dementia-related psychosis and agitation/aggression.

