# 1. INTRODUCTION AND OBJECTIVES

#### 1.1. Introduction

Study MP-101-01(b) is a Phase 2, multicenter, double-blind, 1:1 randomized, parallel, placebo-controlled, 10-week study of MP-101, consisting of screening, treatment, and follow-up periods, in patients with dementia-related psychosis and/or agitation and aggression.

This statistical analysis plan (SAP) describes the analysis variables and statistical procedures that will be used to analyze and report the results from Protocol MP-101-01(b), which was approved on 13 February 2017.

Some of the analyses detailed here may be more explicit or in some aspects different from those stated in the protocol. In case of differences, this SAP supersedes the statistical sections in the protocol.

Changes to the protocol that impact the design, the data collected, or the statistical methods and that occur after the finalization of this SAP may require amendment of the approved SAP. Similarly, changes to the planned analysis variables and/or statistical methods described in the approved SAP may also require amendment of the SAP.

The formats for the tables, listings, and figures described in this SAP are provided in a companion document. Changes to the formats of these reports that are decided after the finalization of the SAP will not require an amendment. In addition, any additional supportive or exploratory analyses requested after SAP approval will not require amendment of the SAP. These additional analyses will be described in the clinical study report (CSR).

See the study protocol for details about the study design, procedures, and schedule of assessments and see the electronic case report form (eCRF) for details about variables collected and their possible values.

The time and events schedule for this study is provided in Section 9.

EMB Statistical Solutions will have responsibility for performing these analyses.

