#### 2.10. Adjustment for Covariates

Where possible, analyses will adjust for the baseline value of the endpoint and by the four baseline randomization strata, i.e.:

- MMSE < 16, eGFR < 60
- MMSE < 16, eGFR  $\ge$  60
- MMSE  $\geq$  16, eGFR < 60
- MMSE  $\geq$  16, eGFR  $\geq$  60

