#### Clinical Global Impression of Improvement (Guy, 1976)

The CGI-I is a 7-point scale that requires the clinician to assess how much the patient's illness has improved or worsened relative to baseline (Visit 2). The scale ranges from 1=very much improved to 7=very much worse.

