## 5.2. Secondary Analyses

Summary statistics of all domains of the NPI will be computed for the observed and change from baseline values in the Evaluable and ITT populations. Summaries of other secondary endpoints will be computed for the observed and change from baseline values in the Evaluable population.

Supporting analyses of the secondary endpoints may be performed stratifying by randomization strata if there are sufficient numbers of patients within each strata.

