#### **Ordinal Endpoints**

The Core Total Score response rate will be analyzed using a one-sided Fisher's Exact test. The lower 95% confidence limit of the difference in Core Total Score response rates (MP-101 minus Placebo) will be will be calculated using an exact unconditional confidence interval. The CGI-I will be analyzed using Cochran-Mantel-Haenszel tests using modified Ridit scores (i.e. van Elteren tests).

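### CGI-I is tested without the Visit 2 CGI-S rating, with no stated sidedness and no between-arm estimate; the test is valid, but precision and a readable effect size are given up

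*Protocol*

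**What the plan says.** The schedules (Protocol section 2, SAP section 9) place CGI-S at Visit 2 only, and CGI-I at Weeks 4, 10 and 11 and at early termination. Neither Protocol 9.1 nor SAP 2.13 describes CGI-S, and no test or model names it. At most it enters the baseline table of SAP 4.3.

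On the CGI-I analysis:

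- Protocol 10.3.3.2: "The CGI-I scores will be analyzed using Cochran-Mantel-Haenszel tests, stratifying by the randomization strata, and using modified Ridit scores".
- SAP 5.2, ordinal endpoints: "The CGI-I will be analyzed using Cochran-Mantel-Haenszel tests using modified Ridit scores (i.e. van Elteren tests". The strata are not repeated, and no sidedness, significance level, estimate or limit is given. The opening of SAP 5.2 makes stratified supporting analyses of secondary endpoints optional.
- SAP 1.1 on precedence: "In case of differences, this SAP supersedes the statistical sections in the protocol".
- SAP 2.10, the general rule: "Where possible, analyses will adjust for the baseline value of the endpoint and by the four baseline randomization strata".
- SAP 2.13: the clinician is to "assess how much the patient's illness has improved or worsened relative to baseline (Visit 2", so CGI-I has no baseline value of its own.

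For comparison, the same paragraph of SAP 5.2 gives Core Total response a one-sided Fisher test and "The lower 95% confidence limit of the difference in Core Total Score response rates (MP-101 minus Placebo". SAP 5.1 treats the primary response rate in the same way, at one-sided 5%. For CGI-I the only other planned output is descriptive: "Summaries of other secondary endpoints will be computed for the observed and change from baseline values in the Evaluable population".

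**The concern.** Among the secondary efficacy outcomes listed in Protocol 10.3.3.2, CGI-I is the only one rated by a clinician. NPI information comes from the caregiver (Protocol 9.1.1), and UPDRS Part III, though investigator-scored, is classed as safety (Protocol 4.2). CGI-I is therefore the natural check on a caregiver-reported primary result.

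Three matters are left open. First, baseline severity is collected with CGI-S but is not used to reduce noise in CGI-I, and the rule in SAP 2.10 has no defined meaning for a scale without a baseline. Second, the p-value that software prints for this test is two-sided, while the primary test is one-sided 5%; the SAP does not say which reading applies to CGI-I. Third, a test alone gives no magnitude with uncertainty to set beside the difference in NPI response rates. If these are settled after unblinding, the covariate and the sidedness become post hoc choices.

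**Working it through.** **The plan's own figure.** The documents give no power or effect size for CGI-I. The only sizing statement is for the primary test (SAP 1.4): 65% versus 35%, 40 evaluable per arm, one-sided 5% Fisher, at least 80% power. Summing the binomial probabilities of all tables with Fisher p ≤ 0.05 gives 79.5% at 40 per arm and 81.1% at 41. Enrolment: 80/(1 − 0.2) = 100. The stated figure is reproduced to within rounding.

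**Direction.** With ridits rank/(n_h + 1) in stratum h, let U_y be the sum over strata of (treated ridit sum minus its expectation) and V_yy its variance. Then Z = U_y/√V_yy, and the two-arm Cochran-Mantel-Haenszel statistic is Z² on 1 df. The sign of Z gives the direction. In simulation at effects of 0.5 and 0.77 SD, no two-sided significant result pointed the wrong way.

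**Cost of a two-sided 5% reading.** Two-sided power = Φ(z_power + 1.645 − 1.960), with z_power taken from the one-sided power.

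- One-sided 80%: Φ(0.842 + 1.645 − 1.960) = Φ(0.526) = 70.1%, a loss of about 10 points.
- One-sided 75%: Φ(0.674 + 1.645 − 1.960) = Φ(0.359) = 64%, a loss of 11 points.
- Simulated van Elteren at 0.5 SD: 66.1% − 53.4% = 12.7 points. The other correlations give 12.7 to 13.4.

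**Gain from CGI-S.** The adjusted statistic is (U_y − bU_x)/√(V_yy − bV_xy), with b = V_xy/V_xx and x the CGI-S ridit. If ρ is the correlation, residual variance falls to about 1 − ρ². Starting from 70% two-sided power (noncentrality 0.524 + 1.960 = 2.484):

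- ρ = 0.3: Φ(2.484/√0.91 − 1.960) = 74.0%
- ρ = 0.5: Φ(2.484/√0.75 − 1.960) = 81.8%

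This formula overstates the gain if ρ describes the latent scales, because cutting both into seven categories weakens the correlation. Simulation allows for that.

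Assumptions, none of them in the documents: latent normal scales cut into 7 categories, four unequal strata, and the effects and ρ shown. Setting A has 36 rated patients per arm, a 0.6 SD effect and 12,000 trials per cell. Setting B has 40 per arm, a 0.5 SD effect and 4,000 trials per cell. Power is at one-sided 5%, van Elteren then CGI-S-adjusted:

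| ρ | A | gain | B | gain |
|---|---|---|---|---|
| 0 | 74.7 / 74.2 | −0.5 | 66.1 / 65.7 | −0.4 |
| 0.2 | 75.2 / 75.8 | +0.6 | 65.4 / 66.2 | +0.8 |
| 0.3 | 75.4 / 77.2 | +1.8 | 66.2 / 67.8 | +1.6 |
| 0.4 | 73.9 / 78.5 | +4.6 | not run | – |
| 0.5 | 75.4 / 82.5 | +7.1 | 66.3 / 74.8 | +8.5 |

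In setting B read two-sided, the gain at ρ = 0.5 is 61.9 − 52.9 = 9.0 points. A further run at 36 per arm and 0.6 SD gave 2 to 3 points at 0.3 and 8 to 9 at 0.5. One-sided type I error stayed between 4.3% and 5.4% for both tests.

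**A larger effect shrinks both figures.** A latent shift of 2 × 0.385 = 0.77 SD corresponds to 65% versus 35%. There, with 40 per arm, van Elteren has 93.6% at ρ = 0.5 and the adjusted test 97.1% (+3.5). The two-sided reading costs 93.1 − 87.2 = 5.9 points at ρ = 0.

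**What an estimate would add.** A Mann-Whitney probability at 0.5 SD is Φ(0.5/√2) = 0.64. Its null standard error at 40 per arm is √(81/(12 × 1,600)) = 0.065, so a 90% interval is roughly ± 1.645 × 0.065 = ± 0.11. No such figure is planned.

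**The case against.** Van Elteren is a sound choice for a seven-point ordinal scale. CGI-I is already a rating of change from Visit 2, and omitting a baseline covariate does not bias a randomised comparison. The endpoint is secondary in a Phase 2 trial with no testing hierarchy (SAP 2.8), so being listed first carries no rank. SAP 1.1 also lets supportive analyses be added without an amendment. All of this stands and limits the weight of the point; an analysis added later is, however, no longer pre-specified.

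The contrast with the rest of the plan is also narrower than it looks. The supporting Cochran-Mantel-Haenszel test in SAP 5.1 has no stated sidedness either, and the mixed models have a limit but no named one-sided test. The clear benchmark is the two Fisher-tested endpoints.

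Four stronger readings are tempting, and the documents do not support them:

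- *The test has no direction.* With two arms it has a signed root.
- *Power is known to be lost by leaving out CGI-S.* The loss depends on a correlation the documents do not give, and is near zero if that is weak.
- *The effect cannot be seen at all.* SAP 5.2 and SAP 8 provide arm-level summaries of CGI-I; only a between-arm estimate with a limit is missing.
- *SAP 2.10 is breached.* Its rule applies where possible and to the endpoint's own baseline, which CGI-I lacks. The rule is silent on CGI-S rather than broken.

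**Conclusion.** The point holds as one of avoidable imprecision and incomplete specification. It is not an invalid analysis. CGI-S is collected at Visit 2 and never used to adjust CGI-I, and SAP 5.2 leaves CGI-I with no sidedness, estimate or limit.

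Leaving out CGI-S costs about 0 to 3 points of power for a correlation up to 0.3 and about 7 to 9 points at 0.5. This assumes latent effects of 0.5 to 0.6 SD and 36 to 40 patients per arm; at 0.77 SD the one-sided gain at 0.5 is nearer 3.5 points. The sidedness cost, about 10 to 13 points where one-sided power is 65 to 80%, arises only if the p-value is read two-sided at 5%. The SAP does not plan that reading; it does not exclude it either. The missing between-arm estimate needs no assumption: it follows directly from the text.

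**What to change.** In SAP 5.2, before unblinding:

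1. Analyse Week 10 CGI-I by stratified rank ANCOVA: the van Elteren test on CGI-I ridits adjusted, within the four MMSE/eGFR strata, for Visit 2 CGI-S ridits. State the strata explicitly, since SAP 5.2 omits them.
2. Report the one-sided 5% p-value from the signed root.
3. Add one between-arm estimate with a 90% confidence interval: either a common odds ratio from a proportional-odds model with treatment, CGI-S and the strata, or a stratified Mann-Whitney probability.
4. Add CGI-S to SAP 2.13, and name it in SAP 2.10 as the baseline covariate for CGI-I.

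This takes a few lines of text and code and no new data. The downsides are about half a point of power if CGI-S proves unrelated to CGI-I, and a proportionality assumption in a small trial if the odds ratio is chosen; the Mann-Whitney probability avoids the latter.

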10.3.3.3. Exploratory Analyses

The exploratory efficacy objectives to determine whether MP-101 is superior to placebo in patient behavior and caregiver burden. Changes in patient behavior will be assessed using NPI domains of depression/dysphoria, elation/euphoria, apathy/indifference, disinhibition, irritability/lability, aberrant motor behavior, sleep and nighttime behavior disorders, and appetite and eating disorders; MMSE.

The ZBI-22 is being utilized to assess caregiver burden.

The exposure-response relationships between efficacy and safety endpoints may also be explored, as needed.

Details of the analyses of exploratory efficacy outcomes will be specified in the SAP

10.3.4. Safety Analyses

10.3.4.1. Adverse Events

All investigational product and protocol procedure AEs will be listed, and if the frequency of events allows, safety data will be summarized using descriptive methodology.

The incidence of symptoms for each treatment will be presented by severity and by association with investigational product as perceived by the investigator. Symptoms reported to occur prior to enrollment will be distinguished from those reported as new or increased in severity during the study. Each symptom will be classified by the most suitable term from the most current version of Medical Dictionary for Regulatory Activities (MedDRA).

The number of investigational product-related SAEs will be reported.

10.3.4.2. Other Evaluations of Safety

Other safety parameters that will be assessed include physical/neurological examinations, safety clinical laboratory parameters, vital signs, and ECG parameters. The parameters will be listed and summarized using standard descriptive statistics. Additional analysis will be performed if warranted upon review of the data.

10.3.5. Pharmacokinetic Analyses

MP-101 and LY2812223 concentrations will be summarized by treatment and time postdose using summary statistics (number, mean, standard deviation, coefficient of variation [CV], minimum, median, maximum, geometric mean, and geometric CV).

For the final analysis, the PK of LY2812223 will be characterized using population PK methods; the effect of renal function on PK will be evaluated. Data from this study may be pooled with data from previous studies. The relationship of LY2812223 concentrations with efficacy and/or safety measures may be explored. The population PK or PK/PD analyses will be performed separately and reported in a population PK report. Other analyses may be performed as needed.

10.3.6. Other Analyses

10.3.6.1. Pharmacogenetics Exploratory Analyses

To explore the effect of genotype on the response to MP-101 in dementia patients, genotype data for HTR2A SNP rs7330461, HTR2A SNP rs6313 (102T/C), APOE, and other genotypes may be analyzed. The analysis methods may be detailed in the SAP.

10.3.7. Interim Analyses

An interim analysis is planned for this trial which will occur after approximately 20 patients have completed Visit 5 (Week 4) to evaluate safety and LY2812223 PK. A second interim analysis may be performed to evaluate the futility of finding differences in the efficacy endpoints between treatment groups. All interim analysis details, including unblinding plans and stopping rules for the futility analysis, will be documented in the Assessment Committee Charter.

Study sites will receive information about interim results ONLY if they need to know for the safety of their patients.

11. References

- Cummings JL. Neuropsychiatric Inventory. Comprehensive assessment of psychopathology in patients with dementia. David Geffen School of Medicine at UCLA. Los Angeles, CA. 2009.

Appendix 1. Abbreviations and Definitions

Term	Definition
5-HT2A/HTR2A	5-hydroxytryptamine (serotonin) 2A (receptor)
AChEI	acetylcholinesterase inhibitors
AD	Alzheimer's disease
ADL	Activity of Daily Living
AE	adverse event: Any untoward medical occurrence in a patient or clinical investigation patient administered a pharmaceutical product that does not necessarily have a causal relationship with this treatment. An adverse event can therefore be any unfavorable and unintended sign (including an abnormal laboratory finding), symptom, or disease temporally associated with the use of a medicinal (investigational) product, whether or not related to the medicinal (investigational) product.
APOE	apolipoprotein E
AST	aspartate aminotransferase
BP	blood pressure
bpm	beats per minute
cAMP	cyclic adenosine monophosphate
CGI-I	Clinical Global Impression of Improvement
CGI-S	Clinical Global Impression of Severity
CI	confidence interval
CKD EPI	Chronic Kidney Disease Epidemiology Collaboration
C _{max}	maximum observed drug concentration
CRF	case report form
CRP	clinical research physician: Individual responsible for the medical conduct of the study. Responsibilities of the CRP may be performed by a physician, global safety physician, or other medical officer.
CSF	cerebrospinal fluid
C-SSRS	Columbia Suicide Severity Rating Scale
СТ	computed tomography

CTCAE Common Terminology Criteria for Adverse Events

complaint A complaint is any written, electronic, or oral communication that alleges deficiencies

related to the identity, quality, purity, durability, reliability, safety or effectiveness, or

performance of a drug or drug delivery system.

CVcoefficient of variation

DSM-V Diagnostic and Statistical Manual of Mental Disorders-Fifth Edition

DP drug product

 EC_{50} half maximal effective concentration

 EC_{100} maximum achievable response concentration

ECG Electrocardiogram

ERB ethical review board

eGFR estimated glomerular filtration rate

enroll The act of assigning a patient to a treatment. Patients who are enrolled in the trial are those

who have been assigned to a treatment.

Patients entered into a trial are those who sign the informed consent form directly or enter

through their legally acceptable representatives.

FDA US Food and Drug Administration

GCP good clinical practice

ΙB Investigator's Brochure

ICF informed consent form

ICH International Conference on Harmonisation

interim analysis An interim analysis is an analysis of clinical study data, separated into treatment groups,

that is conducted before the final reporting database is created/locked.

investigational

A pharmaceutical form of an active ingredient or placebo being tested or used as a reference product

in a clinical trial, including products already on the market when used or assembled

(formulated or packaged) in a way different from the authorized form, or marketed products used for an unauthorized indication, or marketed products used to gain further information

about the authorized form.

IRB investigational review board

IWRS interactive web-response system

mGlu metabotropic glutamate

MAD multiple-ascending dose MedDRA Medical Dictionary for Regulatory Activities

MMSE Mini-Mental State Exam

MRI magnetic resonance imaging

NPI Neuropsychiatric Inventory

NPI-D Neuropsychiatric Inventory-Caregiver Distress

PD Pharmacodynamics

phMRI pharmacological magnetic resonance imaging

PK Pharmacokinetic

PPS per-protocol set: The set of data generated by the subset of patients/who sufficiently

complied with the protocol to ensure that these data would be likely to exhibit the effects of

treatment, according to the underlying scientific model.

QD quaque die (once daily)

QTc corrected QT interval

QTcF Fridericia's corrected QT interval

SAD single-ascending dose

SAE serious adverse event

SAP Statistical Analysis Plan

Screen The act of determining if an individual meets minimum requirements to become part of a

pool of potential candidates for participation in a clinical study.

SNP single nucleotide polymorphism

SUSAR suspected unexpected serious adverse reaction

terminal half-life

TEAE treatment-emergent adverse event: An untoward medical occurrence that emerges during a

defined treatment period, having been absent pretreatment, or worsens relative to the pretreatment state, which and does not necessarily have to have a causal relationship with

this treatment.

 t_{max} time of maximum concentration

TUG Timed Up and Go

ULN upper limit of normal

UPDRS Unified Parkinson's Disease Rating Scale

ZBI-22

Zarit Burden Interview-22

